### **2.6.2 Clinical Model for Study of Stress Effects on Prostate Cancer and Immune Responses**

Studying stress response (SR) in conjunction with the immunotherapy clinical trial offers many advantages for identifying SR and other potential immune modulators. An optional sub-study will be made available for patients being screened to the PROSTVAC therapeutic intervention of this study. The goals of the sub-study will be to address critical empirical questions related to underlying physiological processes within the context of allostatic load (AL), by examining the mechanistic underpinnings of immune and stress responses. AL is an indicator of biological dysregulation in response to psychological and social stress and is used as a marker of psychological and social stressor impact on biological functioning (102). The trial is highly feasible and immune responses are likely to be seen in half or more of subjects, providing a wide range on immune response parameters for comparisons.

The sub-study will be the first to use a biobehavioral model to examine biological, psychological, and behavioral pathways that contribute to disease processes and outcomes in this population. Investigators will do this by characterizing stress reactivity among prostate cancer patients based on both biological factors that include individual variation in genetic variants in the GR receptor gene and chronic SES stressors. The sub-study is unique in seeking to relate stress measurements to clinical and immunologic responses. In addition to having a significant impact in terms of understanding the ways in which biological and psychological pathways may contribute to racial disparities in prostate cancer outcomes, the research is highly relevant to precision medicine.

The optional sub-study will involve correlative analyses will demonstrate another distinct feature by studying the pathways within the setting of a clinical trial of prostate cancer immunotherapy. The clinical trial itself was designed and powered to detect a therapeutic effect in prostate cancer patients. It is not a trial designed to measure an irrelevant immune response in normal volunteers or non-cancer patients. Hence, the psychologic insights will be derived from, and applicable to, a “real world” setting. The PROSTVAC vaccine has been in development for several years, and randomized Phase II trials in patients with advanced disease have shown an improvement in overall survival. The PROSPECT trial, designated by the FDA as the registration trial, completed worldwide accrual in December, 2014. Interim analyses will be made in early 2017, with the hope for FDA approval in late 2017 or early 2018. The present trial focuses on a different population, a minimally-treated population after prostatectomy. The physiologic, and likely psychologic, conditions of these subjects are markedly different from those in the PROSPECT trial. MUSC investigators will make comparisons between measurement of SR and other psychologic parameters, and clinical (relapse-free survival), genomic (IgG allotypes), and immunologic (anti-Forssman antibody, antigen-restricted effector T cell populations) measurements. Thus, if the vaccine turns out not to have the desired clinical effect, the investigators will still be able to examine the relationship between stress and immune response development.

Another important aspect of this clinical trial and optional sub-study will be to define the acceptability of stress reactivity measurements in this patient population. The trial will not be powered to detect subtle differences in SR between racial groups. However, an accurate power analysis to establish recruitment goals for a large-scale trial is not possible without initial data on the acceptability of psychologic testing in men with prostate cancer, and the range of SR values to be expected. Project investigators will use the Trier Social Stress Test (TSST) (103) to induce a stress response among the clinical trial participants. The TSST is a standardized psychological stress challenge which has been used extensively in research studies. A meta-analysis supports that it is the gold standard for evoking an HPA axis stress response in a laboratory setting (104). The ACTH and cortisol changes induced by the TSST reflect the sequence of HPA axis activity. That is, ACTH peaks first, at the end of the 15-minute stressor, and returns to baseline level within 40 minutes. Total plasma cortisol peaks 20 minutes after ACTH, and returns to baseline about an hour after initiation of the stressor. Most of the studies of these tools in cancer patients have been in breast cancer and leukemia survivors. Men may be less willing to accurately share their feelings, to participate in role-playing tests, and to learn coping strategies. Indeed, there are no published studies on the use of the Trier Social Stress Test in men with prostate cancer. The data developed during this study will provide a solid foundation for planning large scale studies and will identify core measures of social, psychological, and behavioral factors that are important to measure as part of precision medicine research and health disparities.

### **3 STUDY OBJECTIVES**

#### **3.1 PRIMARY OBJECTIVE**

The primary objective is to determine if PROSTVAC-V/F has significant anti-tumor effect when used as a post-surgical adjuvant therapy in subjects at high risk of relapse after prostatectomy. The probability of RFS at 2 years after prostatectomy will be compared with RFS data from similar, published, historical patient series.

#### **3.2 SECONDARY OBJECTIVES**

There are four secondary objectives.

- To compare observed RFSs for the study population with the predicted RFSs for the study population. The predicted RFS values will be calculated from each patient's clinical and pathologic data by standard algorithms (Duke and CaPSURE). The observed and predicted RFSs will be presented as Kaplan-Meier plots and comparisons will be performed using the logrank test.
- To compare the observed RFS with the RFSs of a historical comparison group of MUSC prostatectomy patients. These patients will be matched to the experimental group for race, Gleason score, and pathological stage. The observed, historical RFSs will be presented as Kaplan-Meier plots and comparisons will be performed using the logrank test.
- To describe associations between the RFS values and various immunologic, genetic, and biochemical parameters on research blood and tissue specimens.
- To describe the toxicity of PROSTVAC-V/F in this patient population.

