Statistics for Main Study:	
Statistical considerations:
 
Primary Objective: The primary endpoint will be a binary indicator of relapse status at the 2 year follow-up visit. Enrollment and treatment initiation must take place no more than 120 days after prostatectomy. Two-year RFS will be estimated as a proportion with an exact 95% confidence interval. RFS will also be treated as a time-to-event variable and Kaplan-Meier curves will be created; median and 95% confidence intervals will be reported.
 
The data from this trial will be compared with results from historical control data obtained from a multi-institutional database which includes high-risk, post-prostatectomy subjects without adjuvant therapy (n = 243), and from a published clinical trial (n = 98). The estimated 2-year probability of RFS of high-risk subjects after prostatectomy is 0.6. We define an "interesting" improvement in RFS to be 30% (i.e. increase in the probability of RFS from 0.6 to 0.78). Assuming a one-sided alpha = 0.1, with 30 patients in a group, we have 80% power to detect this difference based on an exact binomial test. Thus if among 30 evaluable subjects, at least 24 are recurrence free at 24 months, we will reject the null hypothesis (2-year RFS=0.60) and conclude that the PROSTVAC intervention improves RFS relative to the RFS of similar patients receiving no adjuvant therapy.
 
Secondary objectives: a) A secondary objective will be a comparison of observed RFS times with the predicted RFS times for the treatment cohort using the Duke and CaPSURE nomograms. The comparison will be performed using the logrank test of the observed and predicted RFSs.
 
b) Biochemical and genomic measurements will be graphically displayed to evaluate their distributions. Transformations will be taken as appropriate. Cox regression will be used to estimate hazard ratios measuring the association between these measures and RFS. 95% confidence will be estimated for the hazard ratios as appropriate.
 
c) Toxicities will be tabulated by CTCAE grade and type.

-----------------------------------	--

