## 4 INVESTIGATIONAL PLAN

### 4.1 STUDY DESIGN AND DURATION

This will be a Phase II study of adjuvant PROSTVAC-V/F in subjects at high risk for relapse after radical prostatectomy. The study will be carried out at MUSC and the VAMC. The coordinating center will be at the Sponsor-Investigator Support Unit. Additional sites may be recruited as needed to ensure accrual.

We anticipate a two year period of accrual and an equal period of follow up for each subjects, or approximately four years total, from the point of completions of approvals and contracts.

The study population will be post-prostatectomy patients whose pathology reports documents one or more high risk features, including one or more of the following: pT3b or pT4, pN1, pT3a (without adjuvant radiation), positive margins, pre-operative PSA  $\geq 10$  ng/mL, Gleason score 8-10. Each site PI will be responsible for reviewing all prostatectomy cases to determine the patient's eligibility and interest in participating in the study.

Forty evaluable subjects (total 44 subjects) will be enrolled. Subjects will be treated with PROSTVAC-V/F alone. Subjects will be followed for relapse for two years after prostatectomy.

Prior to any study specific activities, the patient must be aware of the nature of his/her disease and willingly consent to the study after being informed of study procedures, the experimental therapy, possible alternatives, risks and potential benefits. IRB approval of this protocol and accompanying consent is required.

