### 4.2 PATIENT POPULATION

This study will be conducted at MUSC and the VAMC. There are approximately 80 radical prostatectomies performed yearly at MUSC (30% African American), and 70 at the VAMC (70% African American). Both institutions have extensive experience with prostate cancer clinical trials, and investigators have been particularly successful in recruiting African American subjects. Therapeutic trial accruals in the HCC include approximately 25% African American subjects, reflecting a close match to the 30% prevalence of African Americans in the population of South Carolina. This study will aim to enroll equal numbers of African American and Caucasian subjects.

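### The matched historical controls in 3.2 all come from MUSC, so for trial men from the VAMC any hospital difference in relapse would be mixed with the vaccine effect, in either direction

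*Combined protocol and SAP*

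**What the plan says.** Section 3.2 lists, as its second secondary objective: "To compare the observed RFS with the RFSs of a historical comparison group of MUSC prostatectomy patients". On the choice of controls it adds: "These patients will be matched to the experimental group for race, Gleason score, and pathological stage". On the analysis: "The observed, historical RFSs will be presented as Kaplan-Meier plots and comparisons will be performed using the logrank test".

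The trial itself is not confined to MUSC. Section 4.1 states: "The study will be carried out at MUSC and the VAMC", and it allows further sites if accrual needs them. Section 4.2 treats the two hospitals as separate institutions. It gives yearly radical prostatectomy volumes of about 80 at MUSC, 30% in African American men, and about 70 at the VAMC, 70% in African American men. It also sets a racial target: "This study will aim to enroll equal numbers of African American and Caucasian subjects".

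Nothing elsewhere addresses site in this comparison. The opening of section 10, section 10.2.1 and section 7.5.2 describe only the comparison with nomogram-predicted RFS. The synopsis does not list the MUSC comparison among its secondary objectives. No site-stratified, site-adjusted or single-site version of it appears in the plan.

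**The concern.** The treated men come from two hospitals and the controls from one. For every trial man operated on at the VAMC, having received the vaccine and having been treated at the VAMC are the same fact as far as this comparison goes. If untreated relapse differs between the hospitals among men of the same race, Gleason score and stage, the logrank test cannot tell that difference from an effect of PROSTVAC. Possible sources are surgeons, the PSA laboratory, referral patterns, and tumour features that are not matched.

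Matching on race does not remove the problem. Because the VAMC performs most of the prostatectomies in African American men, race matching would mainly pair African American trial men from the VAMC with African American controls from MUSC.

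What is at stake is the interpretation of the only planned comparison with matched local patients, in a trial that aims for equal racial enrolment.

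**Working it through.** The plan gives no site share, sample size or power for this comparison, so there is no figure of its own to reproduce. The check is arithmetic on the volumes in section 4.2.

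**Step 1. Prostatectomies by hospital and race**

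| | MUSC | VAMC | Total | VAMC share |
|---|---|---|---|---|
| All | 80 | 70 | 150 | 70/150 = 46.7% |
| African American | 0.30 × 80 = 24 | 0.70 × 70 = 49 | 73 | 49/73 = 67.1% |
| Other | 80 − 24 = 56 | 70 − 49 = 21 | 77 | 21/77 = 27.3% |

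**Step 2. Effect of the racial target.** Assume equal numbers of African American and Caucasian subjects, recruitment within each race in proportion to hospital volume, and all other men counted as Caucasian. The expected VAMC share is then 0.5 × 67.1% + 0.5 × 27.3% = 47.2%. The target leaves the overall share almost unchanged.

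**Step 3. What a hospital difference would do (illustration only).** The documents give no RFS by site. Assume no vaccine effect and a 2-year RFS of 0.60 in MUSC controls, the planning value in the synopsis ("The estimated 2-year probability of RFS of high-risk subjects after prostatectomy is 0.6"). Assume also the same VAMC-minus-MUSC gap for all VAMC men after matching. Then:

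- apparent difference = VAMC share × gap
- approximate hazard ratio = ln(trial RFS) / ln(0.60), assuming proportional hazards

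| Assumed gap (VAMC − MUSC) | Apparent difference | Trial RFS | Hazard ratio |
|---|---|---|---|
| +5 points | 0.467 × 5 = +2.3 points | 0.623 | 0.93 |
| +10 points | 0.467 × 10 = +4.7 points | 0.647 | 0.85 |
| −5 points | −2.3 points | 0.577 | 1.08 |
| −10 points | −4.7 points | 0.553 | 1.16 |

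**Step 4. Size of a MUSC-only comparison.** With the 30 evaluable subjects of section 10.1, the MUSC men number about 30 × (1 − 0.472) = 15.8, or 16. Of 15 African American subjects, about 15 × 24/73 = 4.9, or 5, would be MUSC men. Section 4.1 still says forty evaluable subjects. The counts would rise in proportion, but the shares in steps 1 and 2 would not change.

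**The case against.** Several points on the other side are sound.

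- **No site difference is shown.** Nothing in the documents says that surgeons, laboratories or relapse rates differ between the hospitals, and both are in Charleston. A reader might infer that the comparison will overstate the vaccine. The documents do not support that: a gap may be absent, and if present it could run either way. This point stands.
- **The counts are of all prostatectomies.** Section 4.2 does not give the high-risk fraction, the consent rate or expected accrual by site, so the enrolled VAMC share could differ from 47%. This also stands. The difficulty remains for as many VAMC men as are enrolled.
- **No false-positive rate can be attached.** It is tempting to convert the shift into a chance of falsely declaring superiority, or to set it against the rise from 0.60 to 0.78. But 3.2 fixes no control group size, matching ratio, significance level or decision rule. The 30 subjects and the 0.60-to-0.78 target belong to the primary binomial test.
- **No race-specific comparison with these controls is planned.** Section 10.3 compares RFS between racial groups within the trial. The 67% figure shows where same-site controls are scarcest; it does not describe bias in a specified result.
- **Better tumour matching would help in part.** Surgical margins and pre-operative PSA are eligibility features in 4.3 but not matching factors. Adding them would reduce differences in case mix, though not differences due to surgeon, laboratory or referral.
- **Follow-up is a weaker argument.** Appendix A sets the visit schedule for trial men at both hospitals. Any contrast with routine historical follow-up affects MUSC men too, and same-site controls would not remove it.

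Finally, this is one of four secondary objectives and no go/no-go decision rests on it. That limits the weight of the point. It does not justify leaving in a confounder that is cheap to remove.

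**Conclusion.** The point holds as a limited, avoidable weakness in one secondary comparison. As written, 3.2 sets trial men from two hospitals against controls from one, does not match on site, and has no analysis in section 10 that separates site from treatment. If enrolment follows the volumes in 4.2, about 47% of trial men and about 67% of African American trial men would lack a same-site control. An assumed gap of 5 or 10 points in untreated 2-year RFS would move the overall comparison by about 2 or 5 points, up or down. The shares rest on accrual proportional to prostatectomy volume; the shifts rest also on a gap that the documents neither state nor imply.

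A reader might go on to doubt the trial's main efficacy conclusion. That does not follow. The primary test uses a fixed 0.60 taken from a multi-centre database and a cooperative-group trial, and the nomogram comparison uses each subject's own predicted RFS. Neither depends on MUSC controls.

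**What to change.** In 3.2, draw the historical controls from both the MUSC and the VAMC prostatectomy series and include site among the matching factors, or stratify the logrank test by site if numbers allow. Write this comparison into 10.2, where it is now missing.

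If VAMC records cannot be used, keep the full comparison, add a sensitivity analysis of MUSC-operated trial men against MUSC controls, and state the site limitation wherever the result is reported. The MUSC-only analysis should not replace the full one, because it would drop about two thirds of the African American subjects.

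The cost is chart abstraction at a hospital already in the trial and somewhat harder matching in about 30 men. The documents do not say whether a usable VAMC series exists, so that needs checking first. The fallback uses data already required for the planned comparison, but its precision would be low: about 16 men, about 5 of them African American under equal racial enrolment.

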### **2.2 BACKGROUND FOR USE OF PROSTVAC-V/F**

#### **2.2.1 High-risk PCa**

PCa is the most common malignancy among men and the second leading cause of cancer death in men in the United States. The lifetime risk of developing PCa in the United States is 1 in 6, whereas the lifetime risk of death due to PCa is 1 in 34. Treatment options for PCa confined to the gland include watchful waiting, prostatectomy, and radiotherapy. While many cases of early and localized PCa can be cured by radical prostatectomy, one third of patients experience a recurrence of disease. These patients can be identified by clinical parameters through the use of widely-available nomograms (1,2). These high-risk features include 1) T3 or T4 primary PCa, 2) one or more lymph nodes containing metastatic PCa, 3) an initial PSA  $\geq 10$  ng/mL, 4) involvement of the seminal vesicles, margins, or extraprostatic tissue with cancer. Subjects with these features are at risk for clinically significant recurrence and poor outcomes.

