#### 4.3 INCLUSION CRITERIA

1. Age  $\geq 21$
2. Completed radical prostatectomy for pathologically-verified adenocarcinoma of the prostate no more than 120 days prior to start of treatment. The following procedures are acceptable: radical retropubic prostatectomy (RRP), laparoscopic radical prostatectomy (with or without robotic assistance; LAPD), radical perineal prostatectomy (RPP).
3. Post-operative PSA  $< 0.2$  ng/mL by 120 days after prostatectomy
4. Must have one or more of the following:
  - pT3b or pT4 primary tumor
  - Gleason score 8-10
  - pN1 lymph node disease
  - positive surgical margins
  - pre-operative PSA of  $\geq 10$  ng/mL
  - presence of any tertiary Gleason 5 component on the prostatectomy pathology report.

**Note:** Patients with pT3a disease who lack one of the above criteria, and who refuse adjuvant radiation, may also be enrolled.

5. ECOG performance status 0-1
6. Adequate hematologic, renal, liver function per parameters in Table 1
7. Subject of fathering potential must agree to use an adequate method of contraception to avoid conception throughout the study and for at least 4 weeks after the last dose of study drug to minimize the risk of pregnancy.
8. Subjects must have had a negative bone scan, and CT of abdomen and pelvis within 26 weeks prior to registration. Additional forms of imaging (Prostascint scan, MRI) may be substituted for a CT scan of the abdomen and pelvis if clinically indicated.

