#### 4.4 EXCLUSION CRITERIA

1. Pure small cell carcinoma of the prostate
2. Radiographically-demonstrable metastases at any time prior to the time of enrollment

3. Diagnosis of cancer requiring systemic therapy in the past 5 years
4. Presence of any major medical condition which, in the opinion of the investigator, precludes participation in the study
5. Neoadjuvant or adjuvant therapy of any kind
6. Chronic administration (defined as daily or every other day for continued use > 14 days) of systemic glucocorticoids within 28 days of the first planned dose of PROSTVAC-V/F. Use of inhaled steroids, nasal sprays, and all topical preparations (creams, solutions, gels, ointments, etc.) for up to 5% of the body surface area is allowed.
7. Use of systemic immunosuppressant agents including anti-metabolites, glucocorticoids, TNF $\alpha$  antagonists, antibodies to IL6 or IL6R, calcineurin inhibitors, mTOR antagonists
8. Prior history of serious toxicity or a systemic reaction to vaccinia immunization such as myopericarditis progressive vaccinia infection, or eczema vaccinatum.
9. Inflammatory or exfoliative skin diseases such as eczema, psoriasis that disrupt epidermis
10. Active infections requiring systemic therapy
11. Serologic evidence of HIV/AIDS.
12. Positive hepatitis C serology or active hepatitis B infection.
13. History of allergy to eggs, egg products, aminoglycoside antibiotics
14. History of myocardial disease, such as myocarditis, cardiomyopathy, congestive heart failure, ischemic cardiomyopathy
15. Prior solid organ or stem cell transplant
16. History of or active autoimmune disease (e.g., autoimmune neutropenia, thrombocytopenia, or hemolytic anemia, systemic lupus, localized lupus, Sjogren's syndrome, scleroderma, myasthenia gravis, Goodpasture's syndrome, or Addison's disease). Persons with vitiligo, Hashimoto's thyroiditis, or Graves disease are not excluded.
17. Vaccination with live attenuated vaccine within 28 days prior to day 1 of PROSTVAC-V/F administration or vaccination with a killed vaccine within 14 days prior to day 1 of PROSTVAC-V/F.

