## 7.5 EFFICACY ASSESSMENTS

Efficacy assessments will primarily be performed by measurement of PSA and by physical assessment. Imaging studies (CT scans of the abdomen and pelvis, and bone scans) will be performed at baseline (up to 16 weeks prior to treatment) and at the end of the study (or within the preceding 2 months before end of study). Otherwise, scans will be performed only if clinically indicated for evaluation of relapse or off study. Additional forms of imaging (Prostascint scan, MRI) may be substituted for a CT scan of the abdomen and pelvis if clinically indicated. However, the imaging method used at baseline will be used for follow up scans. Compliance with therapy may be considered a component of the efficacy assessment. Compliance with PROSTVAC-V/F will be monitored at each visit by interviewing the patient and reviewing the infusion center records for administration.

Both primary and secondary efficacy assessment involve measurement of RFS. Recurrence will be defined as the occurrence of any of the following:

- Institution of new prostate cancer therapy
- First detection of a PSA level  $\geq 0.2$  ng/mL (confirmed  $> 30$  days later) after completion of all PROSTVAC V/F vaccine doses
- Development of radiographically-demonstrable metastases
- Death

RFS at two years will be met if a patient has met none of the above criteria two years post-surgery. RFS as a time to event endpoint will be measured as the time in days from surgery to any of the above conditions being met.

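### The MUSC historical comparison in Section 3.2 matches only on race, Gleason score and stage, so controls can be lower-risk than trial men, and its text does not rule out adjuvant-treated controls

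*Combined protocol and SAP*

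**What the plan says.** Section 3.2 sets the objective: "To compare the observed RFS with the RFSs of a historical comparison group of MUSC prostatectomy patients". The only selection rule is "These patients will be matched to the experimental group for race, Gleason score, and pathological stage". The analysis is given as "The observed, historical RFSs will be presented as Kaplan-Meier plots and comparisons will be performed using the logrank test". No control number, alpha, calendar period or RFS definition for controls is stated. The synopsis, Section 7.5.2 and Section 10.2 do not mention this comparison, so nothing later adds to the rule.

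The trial's own population is narrower. Under Section 4.3, criterion 4, any one of six features is enough for entry. They include "positive surgical margins", "pre-operative PSA of" 10 ng/mL or more, and any tertiary Gleason 5 component. A note adds men with pT3a disease alone who refuse adjuvant radiation. Criterion 3 requires a post-operative PSA below 0.2 ng/mL by 120 days. Section 4.4 excludes "Neoadjuvant or adjuvant therapy of any kind". Section 7.5 lists "Institution of new prostate cancer therapy" among the RFS events and times RFS from surgery.

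**The concern.** A matched historical comparison is informative only if the controls could have entered the trial. Here a man with pT2, Gleason 7 disease, positive margins and a pre-operative PSA of 15 can enroll. The stated rule allows his match to be a pT2, Gleason 7 man with clear margins and a PSA of 5, who would not qualify. Section 2.2.1 itself names PSA of 10 or more and margin involvement as high-risk features. Controls selected this way tend to relapse less, which works against the vaccine.

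Two further gaps would work the other way. Controls with a persistently detectable PSA after surgery are not excluded, although such men could not enter the trial. Nor are controls who had adjuvant radiation or ADT, which Section 2.2.2 describes as the main post-surgical adjuvant treatments. If such men were included and their therapy were scored under Section 7.5, each would fail on the day therapy began.

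At stake is whether a difference, or the lack of one, in this comparison can be attributed to the vaccine rather than to the choice of controls.

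**Working it through.** The plan gives no sample size, power or expected result for this comparison, so there is no figure to reproduce. The check sets the criteria side by side and then sizes each bias under stated assumptions.

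**Entry features against matching factors**

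- pT3b/pT4, pN1 and the pT3a route: covered if pathological stage means full pT and pN, which Section 3.2 does not define.
- Gleason 8-10: covered.
- Tertiary Gleason 5: not named as a matching factor.
- Positive margins and pre-operative PSA of 10 or more: not covered. Section 10.5 records both as items separate from pathologic stage.
- Post-operative PSA below 0.2 and no adjuvant therapy: not stated for controls.

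**Bias 1: lower-risk controls**

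From the plan (Section 10.1): 2-year RFS of 0.60 without adjuvant therapy and a target of 0.78, a gain of 0.18. Assumed: a fraction f = 0.3 to 0.6 of trial men qualify only on unmatched features, and a low-risk match has 2-year RFS of 0.75 to 0.85.

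Excess control RFS = f × (match RFS − 0.60), if every such match is low-risk:

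- f = 0.3: 0.3 × 0.15 = 0.045, to 0.3 × 0.25 = 0.075
- f = 0.6: 0.6 × 0.15 = 0.09, to 0.6 × 0.25 = 0.15

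The range is 4.5 to 15 points. If half of these matches share the features by chance, it halves to about 2 to 7.5 points.

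Effect on power, with a separate assumption that 30% of controls are low-risk with RFS of 0.80 to 0.90: control RFS = 0.7 × 0.60 + 0.3 × 0.80 = 0.66, or 0.42 + 0.3 × 0.90 = 0.69. With a true vaccine RFS of 0.78, an assumed 30 versus 30 men and one-sided alpha 0.10, a two-proportion test has power 0.59 with comparable controls, 0.40 at 0.66 and 0.31 at 0.69.

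**Bias 2: adjuvant therapy scored as relapse**

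Assumed: a share a of controls had adjuvant therapy, unrelated to relapse risk, and Section 7.5 is applied to them. Apparent control RFS = 0.60 × (1 − a). With no vaccine effect and trial RFS of 0.60:

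| a | apparent control RFS | spurious gain | logrank rejection rate |
|---|---|---|---|
| 0% | 0.60 | 0 | 0.10 |
| 10% | 0.54 | 0.06 | 0.23 |
| 20% | 0.48 | 0.12 | 0.44 |
| 30% | 0.42 | 0.18 | 0.67 |

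Rejection rates come from 2,000 simulated trials per row: 30 versus 30 men, one-sided 0.10, exponential relapse times, censoring at 24 months, adjuvant start at 1 to 6 months. At 30% the spurious gain equals the whole target. If adjuvant therapy went mainly to men who would have relapsed anyway, the loss would be smaller.

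**The clock**

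Trial men may start treatment up to 120 days after surgery, and PSA relapse counts only after all doses. The last dose is on study Day 141, which is 140 days after Day 1, so it can fall 120 + 140 = 260 days after surgery (before visit windows). Unless controls follow the same rule, their PSA relapses count during a period in which a trial man's do not.

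**The case against.** The strongest objection concerns adjuvant therapy. The synopsis hypothesis, the opening of Section 10 and Section 10.1 all describe comparison patients as untreated, and Section 10.1 says that none of the 243 men in the sizing database had adjuvant therapy. A reader might infer from Section 3.2 that the plan pools treated men and scores them as immediate failures. The documents do not support that. They show an intention to use untreated controls, they give no RFS definition for the MUSC group, and they do not say that planned adjuvant therapy counts as new therapy. What stands is narrower: none of those statements covers the MUSC group, and the restriction written for the sizing database is missing here.

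The objection to the magnitude also largely stands. The values of f and of match RFS have no source in the documents. Section 2.2.1 says that "one third of patients experience a recurrence of disease", but gives no time horizon, so it cannot anchor a 2-year figure. The 0.60 draws partly on an all-node-positive series, and men entering on margins or PSA alone may do better, which would shrink the gap. The upper end is close to a worst case.

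It is also fair that this is one of four secondary objectives, that even with comparable controls its power at 30 versus 30 is only 0.59, and that the nomogram comparison already uses each man's clinical and pathologic data. These points limit the consequence. They do not correct the matching rule.

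**Conclusion.** The concern holds for the matching rule. Followed as written, it admits controls who would not have qualified for the trial, and this can hide a benefit. Under the assumptions above, the shift is up to about 4.5 to 15 points of 2-year RFS, or roughly half that if half the affected matches share the unmatched features. The adjuvant-therapy gap is conditional: about 6 points per 10% of controls treated, in the vaccine's favour, if such men are included and the trial's RFS definition is applied to them. The biases oppose each other, nothing makes them cancel, and the net direction is unknown.

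A reader might go further and conclude that the objective cannot be answered or that the trial's conclusion is at risk. Neither follows. The objective can be repaired by specifying the controls properly, and the primary exact binomial test against 0.60 does not use the MUSC group.

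**What to change.** In Section 3.2, and as a new paragraph in Section 10.2:

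- Draw controls only from men who meet inclusion criteria 3 and 4, including the pT3a note.
- Exclude neoadjuvant therapy, and adjuvant therapy defined as treatment started before any relapse criterion (PSA or imaging) was met. A man treated after relapse stays in the pool and counts as an event. Without this definition, early failures could be dropped and control RFS inflated. Report how many men the exclusion removes and when their therapy began.
- Match on, or adjust for, margin status and pre-operative PSA (under 10 versus 10 or more) in addition to race, Gleason score and stage. Say whether stage includes pN. If exact matches run out, keep the eligibility restriction and adjust.
- Apply the trial's RFS definition to controls. Require each control to be relapse-free at a landmark equal to his matched trial man's surgery-to-treatment interval (at most 120 days), and count PSA relapse from the same time after surgery. State which date applies when a trial man does not complete all doses.

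The cost is protocol wording, some extra chart abstraction and a smaller control pool. Sections 7.1 and 10.5 already provide margins and PSA for trial men. Their availability for MUSC controls is not stated and should be checked before the rule is fixed. Because the controls are historical, the change affects no subject's treatment or visits, and it should be made before controls are selected.
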